# EORTC QLQ-MY20

This questionnaire contains 20 questions organized into 2 functional scales and 2 symptom scales. As with the QLQ-C30, the analysis of the QLQ-MY20 scales will be summarized using descriptive statistics including mean, standard deviation, 95% CI, median, minimum, maximum at each timepoint. This will be done based on the observed values as well as change from baseline values.

# EORTC QLQ-CIPN20

This questionnaire contains 20 questions which can be grouped into a sensory subscale (9 items), motor subscale (8 items) and autonomic subscale (3 items). The analysis of the QLQ-CIPN20 subscales will consist of descriptive statistics based on observed values and change from baseline values. Number and percent will be summarized for the item-level responses at each visit.

#### EQ-5D Index

Analysis of the EQ-5D index will consist of descriptive statistics based on observed values and, separately, based on change from baseline.

# EQ-VAS

Analysis of EQ-VAS will consist of descriptive statistics based on observed values and separately, based on change from baseline.

# PGIS/PGIC

Analysis of the PGIS and PGIC will be included in the supplementary PRO analysis plan.

# 6.4.5. Healthcare Resource Utilization

Healthcare resource use data, including hospitalization data (including type of hospitalization, length of stay, ICU admissions), transfusions, infections and outpatient visits may be summarized and listed. Length of first dose (C1D1) and second dose (C1D4) hospitalizations will be summarized.

# 6.5. Subset Analyses

All the subset analyses will be exploratory; no adjustment for multiplicity will be performed. Analyses will only be performed if there is sufficient sample size. The determination of whether or not there is sufficient sample size will be defined after enrollment is complete and prior to database lock. As a general rule, time to event analyses will not be performed on subgroups unless there are  $\geq 10$  events and  $\geq 5\%$  of participants overall within the defined subset and analyses of ORR will only be performed if there are  $\geq 10$  participants overall within the defined subset. Deviations from these analyses will be described in the clinical study report.

The following subset analyses will be performed for ORR by BICR based on the Safety Analysis Set:

- Baseline cytogenetics (high risk vs standard risk);
- Baseline bone marrow plasma cells (<50% vs  $\ge 50\%$ );
- Prior stem cell transplant (yes vs no);
- Disease stage (1-2 vs 3);
- Number of prior lines  $(\leq 5, >5)$ ;
- Type of myeloma (IgG vs non-IgG vs light chain only);
- Age (<65 vs  $\geq$ 65; <75 vs  $\geq$ 75);
- Sex (Male vs Female);
- Race (White vs others);
- Renal function (CrCl ≤60 mL/min vs >60 mL/min);
- Liver function normal (AST and total bilirubin ≤ ULN) vs impaired (AST or total bilirubin > ULN);
- Refractory to last therapy (yes vs no);
- Penta refractory (yes vs no);
- ECOG (0 vs 1-2);

• For cohort B, type of prior BCMA-targeted therapy (ADC, CAR-T) and presence of EMD (yes vs no).

ORR in subsets will be presented in a forest plot.

Other subgroups of race may be summarized, if data permits. The subset analyses may also be performed for ORR based investigator assessment.

#### 6.6. Baseline and Other Summaries and Analyses

#### 6.6.1. Baseline Summaries

Analyses of baseline data will be based on the Safety Analysis Set and will be displayed by cohort and overall.

#### 6.6.1.1. Demographic and Baseline Characteristics

The following demographic and baseline characteristics will be summarized by number and percentage:

- Gender (male, female);
- Age;
  - 18 to <65; 65 to <75; ≥75;
  - $<65 \text{ vs} \ge 65;$
  - <75 vs  $\geq$ 75;
- Race (White, Black or African American, Asian, American Indian or Alaska Native, Native Hawaiian or other Pacific Islander, Not Reported, Unknown) and ethnicity (Hispanic, not Hispanic, Not reported);
- Geographic Region (North America, Europe, Asia, Other).

Age (continuous), height (cm), weight (kg), BMI (kg/m^2) will be summarized with descriptive statistics.

#### 6.6.1.2. Medical History

Medical history will be coded using the most current version of MedDRA and summarized by MedDRA's SOC and PT from the 'Medical History' CRF page. Each participant will be counted only once within each PT or SOC. Summaries will be ordered by alphabetical SOC and PT in descending order of overall frequency in two cohorts combined. In case of equal frequency, alphabetical order will be used. Separate summaries will be provided for past, present, or either condition.

# 6.6.1.3. Disease Characteristics

The following baseline disease characteristics will be summarized by number and percentage:

- Current disease stage by Revised Multiple Myeloma International Staging System (R-ISS, Stage I, II, and III, or unknown);
- Eastern Cooperative Oncology Group (ECOG) Performance status (ie, 0, 1, 2);
- Cytogenetics (including high risk vs standard risk);
- Presence of EMD (target lesions vs non-target lesions only excluding bone vs no) by investigator and BICR, separately;
- Number of bone lesions (1-4, vs 5-10, vs >10) for those with non-target bone lesions only;
- Baseline bone marrow plasma cells (<50% vs  $\ge 50\%$ );
- Type of myeloma (IgG vs non-IgG [IgA, IgD, IgE, IgM] vs light chain only [kappa light chain, lambda light chain]);
- Type of measurable disease at baseline (see Section 5.2.9):
  - Serum M-protein;
  - Urine M-protein;
  - Serum free light chain (if not measurable by serum or urine);
- Renal function (CrCl ≤60 mL/min vs >60 mL/min);
- Liver function normal (AST and total bilirubin ≤ ULN) vs impaired (AST or total bilirubin > ULN [including both AST and total bilirubin >ULN]).

The following baseline disease characteristics will be summarized by descriptive statistics :

- Time since first diagnosis (months), defined as (date of first dose of study intervention date of first diagnosis) / 30.4375;
- Time since onset of current episode (months), defined as (date of first dose of study intervention- date of onset of current episode) / 30.4375.

#### 6.6.1.4. Prior Anticancer Therapy

The prior anticancer therapies are collected under the 'Response to Regimen' and 'Prior Transplant Details' (PRIOR TPLT) eCRF pages.

The number and percentage of participants in each of the following anticancer therapy categories will be tabulated:

- Participants with prior IMiDs and type (eg, lenalidomide, pomalidomide, or thalidomide);
- Participants with prior PI and type (eg, bortezomib, carfilzomib, ixazomib);
- Participants with prior anti-CD38 mAb and type (eg, daratumumab, isatuximab);
- Participants who are refractory to their last line of therapy;
- Participants who are triple-class refractory (refractory to at least 1 of each type above);
- Participants who are penta-drug exposed (have received at least 2 IMIDs, 2 PIs and 1 anti-CD38);
- Participants who are penta-drug refractory (refractory to 2 IMIDs, 2 PIs and 1 anti-CD38);
- Participants with prior stem cell transplant and type (autologous, allogeneic, or syngeneic);
- For cohort B, type of prior BCMA-targeted therapy (ADC, CAR-T, both).

Prior anticancer drug therapy will be summarized as follows based on the number and percentage of participants:

- Number of prior anticancer therapy lines (descriptive statistics, as well as broken down in categories by the number of prior lines);
- Best overall response on the last prior anticancer therapy line received;
- Reason for stopping the last prior therapy.

The prior anticancer drugs will be coded in the WHO Drug coding dictionary and will be summarized based on the number and percentage of participants by PT. A participant will be counted only once within a given PT, even if he or she received the same medication at different times. The summary will be sorted in descending order of the overall frequency in two cohorts combined. In case of equal frequency, alphabetical order will be used.

#### 6.6.2. Study Conduct and Participant Disposition

#### 6.6.2.1. Disposition

The percentages below will be calculated based on the number of participants in the Safety Analysis Set (unless specified otherwise) and summarized by cohort and overall.

- Number of participants enrolled and treated by country and site;
- Number and percentage of participants in each of the analysis sets defined in Section 4 based on all enrolled participants;
- Number and percentage of enrolled participants with study intervention ongoing, discontinued or not given;
- Number and percentage of enrolled participants who discontinued study intervention, overall and by the main reason for discontinuation of study intervention;
- Number and percentage of participants who discontinued follow-up, overall and by the main reason for discontinuation of follow-up. Participants without a follow-up disposition CRF who died, were lost to follow-up, or withdrew consent during treatment will have their treatment discontinuation reason displayed as their follow-up discontinuation reason.

In addition, dispositions related to COVID-19 may be presented in a separate listing if there is significant impact of COVID-19.

# 6.6.2.2. Protocol Deviations

Potentially important protocol deviations will be compiled prior to database closure and will be summarized by category (n[%]) for the Safety Analysis Set by cohort and overall.

In addition, protocol deviations related to COVID-19 may be presented in a separate listing if there is significant impact of COVID-19.

#### 6.6.3. Study Intervention Exposure

Exposure will be summarized based on the Safety Analysis Set.

Elranatamab is administered as a subcutaneous injection at 76 mg once every week on Days 1, 8, 15 and 21 of each 28-day cycle. Elranatamab is also administered on C1D4. A minimum of 2 days should be maintained between the 2 step-up priming doses (C1D1 and C1D4) and a minimum of 3 days between C1D4 dose and the first full dose (C1D8); a minimum of 6 days should be maintained between doses thereafter. The dose of elranatamab should be increased to 76 mg on C1D8 as long as the participant meets the criteria listed in Protocol Section 6.6.1. If a participant does not meet these criteria on C1D8, initiation of dosing with 76 mg should be deferred until the criteria are met. In addition, if a participant has received QW dosing for at least 6 cycles and has achieved an IMWG response category of PR or better persisting for at least 2 months, the dose interval will be changed from QW to Q2W. If the participant subsequently begins to have an increase of disease burden not yet qualifying as PD according to IMWG criteria, dose intervals should return to weekly dosing. If the dose interval is changed, cycles should remain the same length (ie, 4-week cycles).

The summary of treatment exposure elranatamab will include the following information:

• Treatment duration (months);

- Number of cycles started per participant (mean, median, min, max);
- Number and percent of participants starting a cycle (any cycle, 1, 2, 3, 4, 5, 6, 7, 8, 9, 10, 11, ≥12-<18, ≥18-<24, ≥24 cycles);
- Total cumulative dose (mg);
- Overall dose intensity (mg/week);
- Overall relative dose (%);
- Overall relative dose intensity (%);
- Number and percent of participants who received 44 mg on the C1D1 visit;
- Number and percent of participants who received 32 mg on the C1D4 visit;
- Number and percent of participants who received 76 mg on the C1D8 visit;
- Number and percent of participants after 6 cycles who switched from QW to Q2W;
- Number and percent of participants, among those switching from QW to Q2W, who switched back to QW.

The treatment duration of elranatamab (in weeks) during the study for a participant is defined as:

Treatment duration (months) = (last dose date – first dose date + 1)/30.4375

The total cumulative dose (mg) of elranatamab is the sum of the actual doses that the participant received during the study; the cumulative dose (mg) of elranatamab per cycle is the sum of the actual doses that the participant received within that cycle (ie, total dose administered [mg]).

Planned treatment duration is needed to calculate dose intensity (DI) and relative dose intensity (RDI). It is defined as follows:

• Planned treatment duration (weeks) = (number of cycles started x 4) - (number of weeks in the last cycle after permanent treatment discontinuation or data cutoff for those on-treatment).

The DI, relative dose (RD), and the RDI will be calculated for each participant overall across all cycles and also for each individual cycle as follows:

• Overall DI (mg/week) = Total cumulative dose (mg)/(last zero/non-zero dose date – first dose date)/7 + (1 if on QW or 2 if on Q2W). If C1D4 is the last visit, duration is 1 week if C1D4 occurred by then;

- Overall Planned DI (mg/week) = Total planned dose (mg)/ Planned treatment duration (weeks);
- Cycle DI (mg/week) = Total cumulative dose for a given cycle (mg)/Actual cycle duration (weeks);
- Cycle Planned DI (mg/week) = Total planned dose for a given cycle (mg)/4 weeks.

The total planned dose for a given cycle is defined as

- Cycle 1: Planned dose (mg/cycle) =  $12+32+76 \times 3$
- After Cycle 1:
  - If the participant is on QW dosing schedule for the cycle:

Planned dose (mg/cycle) =  $76 \times 4$ 

• If the participant is on Q2W dosing schedule for the cycle:

Planned dose (mg/cycle) =  $76 \times 2$ 

For last cycle, subtract planned doses after a participant permanently discontinues treatment or data cutoff for those on-treatment.

The total planned dose is the sum of the total planned dose across all cycles.

The RD and RDI are defined as follows:

- Cycle RD (%) = [Total given dose for a given cycle (mg) / Total planned dose for a given cycle (mg)] × 100;
- Overall RD (%) = [Total cumulative dose (mg) / Total planned dose (mg)]  $\times$  100;
- Cycle RDI (%) = [Cycle DI (mg/week) / Cycle Planned DI (mg/week)] × 100;
- Overall RDI (%) = [Overall DI (mg/week) / Overall Planned DI (mg/week)] × 100.

Cycle DI and Cycle RDI will be summarized and plotted vs time (weeks).

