### 5.2.5. Definition of Cycle and Cycle Day

Cycle start and end dates are derived per participant. The definition for each cycle is driven by study drug elranatamab. Elranatamab is administered on Days 1, 8, 15 and 22 of each 28-day cycle. As described in Protocol Section 6.1.1, if a participant has received QW dosing for at least 6 cycles and has achieved an IMWG response category of PR or better persisting for at least 2 months, the dosing interval will be changed from QW to Q2W. If the participant subsequently begins to have an increase of disease burden not yet qualifying as PD according to IMWG criteria, dose intervals should return to weekly dosing. If the dose interval is changed, cycles should remain the same length (ie, 4-week cycles). In either dosing scenario, the nominal cycle length is 28 days.

- For Cycle 1, the actual cycle starts date is the date each participant receives the first non-zero study intervention;
- For all other cycles, the actual cycle start date for each participant is the earliest start date of dosing in the Cycle X Day 1 visit CRF exposure page;
- For all but the last cycle;
  - Actual cycle stop date is calculated as the start date of the next cycle minus 1 day;
  - Actual cycle duration is calculated from Day 1 of a cycle to the day prior to Day 1 of the next cycle, as follows:

Actual Cycle Duration (weeks) = (cycle stop date – cycle start date + 1)/7

• For the last cycle, actual cycle duration is based on the actual cycle stop date which is last zero/non-zero dose date + (7 days if on QW or 14 days if on Q2W) – 1 day. If C1D4 is the last visit, cycle stop date is Day 7 if C1D4 occurred by then.

The cycle day will be calculated as:

Cycle day = Date of the assessment/event – cycle start date + 1.

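### SAP 6.6.3 prints the Overall dose intensity formula without a bracket around the duration in weeks, so taken literally it gives an RDI of about 3% to 6% for a fully dosed participant (minor).

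*SAP*

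**What the plan says.** SAP 6.6.3 lists Overall DI and Overall RDI among the exposure summaries. The Overall DI line begins "Total cumulative dose (mg)/(last zero/non-zero dose date – first dose date)/7" and continues, in the same expression, "first dose date)/7 + (1 if on QW or 2 if on Q2W"). It is followed by a special case: "If C1D4 is the last visit, duration is 1 week if C1D4 occurred by then".

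The comparator is "Overall Planned DI (mg/week) = Total planned dose (mg)/ Planned treatment duration (weeks"), and the ratio is "Overall RDI (%) = [Overall DI (mg/week) / Overall Planned DI (mg/week)] × 100". For a participant who completes every cycle started, planned duration is four weeks per cycle.

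SAP 5.2.5 handles the same end-of-treatment interval in dates. The stop date of the last cycle is "last zero/non-zero dose date + (7 days if on QW or 14 days if on Q2W) – 1 day", and cycle duration in weeks is (stop − start + 1)/7.

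**The concern.** The Overall DI line has no bracket enclosing the exposure time in weeks. Evaluated left to right, the 7 acts as a further divisor of the dose instead of converting days to weeks, and the final dosing interval is added to the dose intensity instead of to the duration. The last step adds weeks to mg/week, so the printed line cannot be right on dimensional grounds.

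At stake are two listed outputs. Overall DI is reported directly, and Overall RDI is computed from it. A literal implementation would be conspicuous. A half-repaired one, dividing by weeks and then adding 1, would give figures that look believable and are still wrong, most of all for participants with short exposure.

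**Working it through.** The SAP states no numeric DI or RDI, so there is no figure of its own to reproduce. The check is whether a participant who receives every planned dose on time gets RDI = 100%.

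**Inputs**
- Planned dose (SAP 6.6.3): Cycle 1, 12 + 32 + 3 × 76 = 272 mg; later QW cycle, 4 × 76 = 304 mg; Q2W cycle, 2 × 76 = 152 mg.
- Dosing days (SAP 5.2.5): "Elranatamab is administered on Days 1, 8, 15 and 22 of each 28-day cycle". On QW, the last dose falls 28 × cycles − 7 days after the first.
- For Q2W cycles I assume dosing on Days 1 and 15, so the last dose falls 28 × (cycles − 1) + 14 days after the first.
- Planned duration: 4 weeks per completed cycle.

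Let D be cumulative dose (mg), T the days from first dose to last dose record, and k = 1 (QW) or 2 (Q2W).

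**Duration implied by SAP 5.2.5.** On QW, stop = last + 7 − 1. Duration is then (last + 7 − 1 − start + 1)/7 = (last − start)/7 + 1. On Q2W the same algebra gives (last − start)/7 + 2. Counted from the first dose, this is T/7 + k, so k belongs inside the divisor.

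**Six full QW cycles.** D = 272 + 5 × 304 = 1792 mg; T = 6 × 28 − 7 = 161 days; planned DI = 1792/24 = 74.67 mg/week.
- As printed, D/T/7 + k: 1792/161/7 + 1 = 2.59 mg/week; RDI = 2.59/74.67 = 3.5%.
- Half repaired, D/(T/7) + k: 1792/23 + 1 = 78.91 mg/week; RDI 105.7%.
- Bracketed, D/(T/7 + k): 1792/(23 + 1) = 74.67 mg/week; RDI 100%.

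**Other fully dosed schedules**

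| Cycles | D (mg) | T (days) | As printed (mg/week) | RDI as printed | Bracketed = planned (mg/week) |
|---|---|---|---|---|---|
| 1 QW | 272 | 21 | 2.85 | 4.2% | 68.00 |
| 2 QW | 576 | 49 | 2.68 | 3.7% | 72.00 |
| 12 QW | 3616 | 329 | 2.57 | 3.4% | 75.33 |
| 24 QW | 7264 | 665 | 2.56 | 3.4% | 75.67 |
| 6 QW + 1 Q2W | 1944 | 182 | 3.53 | 5.1% | 69.43 |
| 6 QW + 6 Q2W | 2704 | 322 | 3.20 | 5.7% | 56.33 |
| 6 QW + 18 Q2W | 4528 | 658 | 2.98 | 6.3% | 47.17 |

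The bracketed form gives RDI of exactly 100% in every row. The half-repaired form is worst at short exposure: after one QW cycle it gives 272/3 + 1 = 91.67 mg/week against a planned 68, or 134.8%.

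**Very short exposure.** If C1D1 is the only dose record, T = 0 and the printed form is 12/0, undefined; the bracketed form gives 12/(0 + 1) = 12 mg/week. If C1D4 is the last visit (on Day 4), the SAP's special case sets duration to 1 week, giving 44/1 = 44 mg/week. The bracketed formula alone would use 3/7 + 1 = 1.43 weeks, so that sentence must stay.

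SAP 6.6.3 names Day 21 where SAP 5.2.5 names Day 22. Using Day 21 for six QW cycles gives 1792/160/7 + 1 = 2.60 mg/week, which changes nothing of substance.

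**The case against.** **The bracket may have been lost when the PDF was read.** Minus signs have visibly dropped out of other SAP formulas: age in 5.2.12, time since diagnosis in 6.6.1.3 and creatinine clearance in 6.7.3. This possibility stands and cannot be excluded. It is not the likelier explanation, because both halves of one outer pair would have to vanish while the inner parentheses of the same line and the square brackets of all four relative dose and RDI formulas survived.

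**The intent is plain.** The C1D4 sentence calls the divisor a duration, Cycle DI divides by a duration in weeks, and SAP 5.2.5 gives the same rule in dates. An output near 2.6 mg/week for a 76 mg weekly dose would be hard to miss. This stands, and it is why the point is minor. It does not remove the need for a correction, because the half-repaired reading passes a casual check.

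**The consequence is limited.** A reader might infer that the trial's tolerability assessment rests on these figures. The documents do not support that: the safety endpoints in SAP 3.2.2 are adverse events, laboratory abnormalities and CRS/ICANS grade. Overall DI and Overall RDI are two of twelve items in a descriptive list, and no test or hold rule uses them.

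**Single-dose participants.** A reader might also infer that the formula fails for everyone who received one dose. It does not. It uses the last zero or non-zero dose record, so a later visit recorded as zero gives a positive divisor, and the C1D4 rule covers those whose last visit is C1D4. Only a sole C1D1 record produces division by zero.

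**Conclusion.** The Overall DI formula in SAP 6.6.3, as printed, is wrong. For fully dosed participants it returns about 2.6 to 2.9 mg/week on QW (RDI about 3.4% to 4.2%) and about 3.0 to 3.5 mg/week after a Q2W switch (RDI about 5% to 6%), where RDI should be 100%. It is undefined when C1D1 is the only dose record.

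The effect is confined to the descriptive Overall DI and Overall RDI summaries. Treatment duration, cumulative dose, Overall RD, Cycle DI, Cycle RD, Cycle RDI and all efficacy analyses are unaffected. The documents do not show how the formula was programmed, so they give no ground for saying that any reported exposure figure is wrong.

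The sizes assume on-schedule full dosing, completed 28-day cycles, and Days 1 and 15 for Q2W. The conclusion also assumes that the printed brackets are those of the source document. Severity: minor.

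**What to change.** Replace the Overall DI expression with:

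Overall DI (mg/week) = total cumulative dose (mg) / { [(date of last zero or non-zero dose − date of first dose)/7] + k }, with k = 1 on QW and k = 2 on Q2W.

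Keep the existing sentence that sets duration to 1 week when C1D4 is the last visit. Check that the analysis program uses the bracketed divisor, for example by confirming that a fully dosed six-cycle QW record returns 74.67 mg/week and RDI 100%.

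The cost is one line of SAP text and a short program check. No data collection, endpoint or clinical rule changes, and 6.6.3 then agrees with 5.2.5.

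### In a last cycle shorter than 4 weeks, Cycle RDI divides a truncated planned dose by a full 4 weeks, so full compliance reads as 133% to 400%

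*SAP*

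**What the plan says.** Four rules in SAP 6.6.3 and 5.2.5 meet in the last cycle.

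- Actual intensity (6.6.3): "Cycle DI (mg/week) = Total cumulative dose for a given cycle (mg)/Actual cycle duration (weeks"). For the last cycle, 5.2.5 sets the stop date at "last zero/non-zero dose date + (7 days if on QW or 14 days if on Q2W"), minus 1 day, with a special case: "If C1D4 is the last visit, cycle stop date is Day 7 if C1D4 occurred by then".
- Planned dose (6.6.3): "For last cycle, subtract planned doses after a participant permanently discontinues treatment or data cutoff for those on-treatment".
- Planned intensity (6.6.3): "Cycle Planned DI (mg/week) = Total planned dose for a given cycle (mg)/4 weeks".
- The ratio (6.6.3): "Cycle RDI (%) = [Cycle DI (mg/week) / Cycle Planned DI (mg/week)] × 100".

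SAP 6.6.3 ends by committing to summarise Cycle DI and Cycle RDI and to plot both against time in weeks. For the overall measures, the same section does shorten the planned treatment duration. It subtracts the weeks of the last cycle that fall after permanent discontinuation or cutoff.

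**The concern.** In the last cycle, the dose given is divided by a duration that may be as short as 1 week. The planned dose is cut back to match what could have been given, but it is still spread over 4 weeks. Planned intensity is therefore too low and Cycle RDI too high whenever the last cycle ends early. Nothing elsewhere in the SAP corrects this, so a programmer who follows the text will produce these values.

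At stake is how the cycle-level table and plot read. A participant who missed or reduced doses just before stopping could appear fully dosed or overdosed in that cycle.

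**Working it through.** **Inputs.** Duration in weeks is ("cycle stop date – cycle start date + 1)/7" (SAP 5.2.5). With the cycle starting on Day 1 and the last dose record on Day d, the last cycle lasts (d + 6)/7 weeks on QW and (d + 13)/7 weeks on Q2W. A cycle whose last visit is C1D4 lasts 7/7 = 1 week. Planned doses (SAP 6.6.3) are 12 + 32 + 76 × 3 = 272 mg in Cycle 1, 76 × 4 = 304 mg on QW and 76 × 2 = 152 mg on Q2W. The documents print no RDI value to reproduce.

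**Baseline check.** Complete cycles behave properly: 68/68, 76/76 and 38/38 mg/week for Cycle 1, QW and Q2W, each 100%.

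**Last cycle, full compliance.** Dose given equals planned dose kept, so

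Cycle RDI = (dose/actual weeks)/(dose/4) × 100 = 4/actual weeks × 100.

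| Last dose in last cycle | Dose (mg) | Actual weeks | Cycle DI (mg/week) | Cycle Planned DI (mg/week) | Cycle RDI |
|---|---|---|---|---|---|
| QW, Day 1 | 76 | 1 | 76 | 19 | 400% |
| QW, Day 8 | 152 | 2 | 76 | 38 | 200% |
| QW, Day 15 | 228 | 3 | 76 | 57 | 133% |
| QW, Day 22 | 304 | 4 | 76 | 76 | 100% |
| Q2W, one dose | 76 | 2 | 38 | 19 | 200% |
| Q2W, two doses | 152 | 4 | 38 | 38 | 100% |
| C1D1 only | 12 | 1 | 12 | 3 | 400% |
| C1D4 | 44 | 1 | 44 | 11 | 400% |
| C1D8 | 120 | 2 | 60 | 30 | 200% |
| C1D15 | 196 | 3 | 65.3 | 49 | 133% |

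Cycle RD is 100% in every row. The C1D1-only row requires discontinuation before the planned C1D4 dose. If discontinuation falls on Days 5 to 7, the planned dose kept is 44 mg and Cycle RDI is 12/(44/4) = 109%. The delivered share is 12/44 = 27%, again inflated fourfold.

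**Last cycle, incomplete delivery.**

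- QW, Day 1 given, zero-dose record on Day 8, then discontinued: 76/2 = 38 against 152/4 = 38, so Cycle RDI is 100%. Half the planned dose was missed (Cycle RD 76/152 = 50%), and the factor 4/2 hides it.
- QW, one dose of 44 mg (a reduced level in Protocol Table 3), then stopped: 44/1 against 76/4 = 19, so Cycle RDI is 232%. Over a matching week it is 44/76 = 58%.

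**Contrast with the overall measure.** Take a participant whose only cycle ended at C1D4, and count three whole weeks as falling after discontinuation. Planned duration is 1 × 4 − 3 = 1 week, so Overall RDI is (44/1)/(44/1) = 100%, while Cycle 1 RDI on the same data is 400%. With five complete QW-schedule cycles (Cycle 1 included) plus one dose in Cycle 6, the total is 272 + 4 × 304 + 76 = 1564 mg over 21 actual and 6 × 4 − 3 = 21 planned weeks, again 100%. Both checks read the Overall DI denominator with brackets around its duration, which the printed formula lacks; that is a separate matter.

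**The case against.** The algebra is not in dispute; the objections concern reach, masking and remedy.

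- **Reach.** Everyone has a last cycle, so a reader might infer that everyone's value is distorted. The documents do not support that: a QW last cycle reaching Day 22, or a Q2W last cycle with two doses, gives exactly 100%. On Q2W the compliant ceiling is 200%. The bulleted exposure summary in SAP 6.6.3 lists only overall intensity measures, and none of them uses the 4-week divisor. This stands.
- **Masking.** A reader might infer that reductions and missed doses would go unseen. SAP 6.6.3.1 reports reductions, interruptions and delays separately, without Cycle RDI. Nor is the cycle measure always wrong. With Day 1 given, zero-dose records on Days 8, 15 and 22, then discontinuation, it gives (76/4)/(304/4) = 25%, which is right. This stands too, but it does not rescue last cycles shorter than 4 weeks.
- **Average effect.** A reader might infer that displayed cycle means will exceed 100%. That depends on how many participants are in a short last cycle at each point and on which day they stopped, and the documents give neither. SAP 5.2.13 also calls for medians, quartiles and extremes. If few values are affected, the median would move little and a 400% maximum would stand out.
- **Remedy.** Counting planned weeks to the calendar date of discontinuation or cutoff would not be enough. Suppose a compliant QW participant is dosed on Day 1 and the cutoff is Day 3. Planned duration would be 3/7 week, planned intensity 76/(3/7) = 177 mg/week, and Cycle RDI 76/177 = 43%. The error would be reversed. SAP 6.6.3 does not say how those weeks are counted, so this objection shapes the fix below.

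**Conclusion.** The definition is inconsistent and should be corrected before these outputs are programmed. For a last cycle shorter than 4 weeks, Cycle RDI is multiplied by 4/actual weeks: 4, 2 or 1.33 on QW, 2 on Q2W, and 4 for a Cycle 1 ending at C1D4, or at C1D1 if discontinuation precedes the planned C1D4 dose. These sizes assume dosing on the nominal days, truncation before the next planned dose, and a zero-dose record for any missed dose.

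The consequence is limited to a secondary descriptive measure: Cycle Planned DI, Cycle RDI, and the RDI summary and plot. This line does not touch full-length last cycles, Cycle RD, Overall RD, Overall RDI, the dose reduction, interruption and delay summaries, or any efficacy analysis.

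**What to change.** In SAP 6.6.3, replace the fixed 4-week divisor in Cycle Planned DI with the planned duration of that cycle:

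- completed cycles: 4 weeks;
- last cycle: the total of the dosing intervals belonging to the planned doses kept after truncation. Each QW dose counts 1 week and each Q2W dose 2 weeks. C1D1 and C1D4 together count 1 week, as does C1D1 alone.

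This matches the rule in SAP 5.2.5 that ends the last cycle 7 or 14 days after the last dose record, less a day, and it returns 100% in every row of the table. In the Day 3 cutoff example, planned duration becomes 1 week and Cycle RDI 100%. In the missed Day 8 example, it becomes 38/(152/2) = 50%.

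Also state that the weeks subtracted from the last cycle in planned treatment duration are counted in the same way, so that the overall and cycle measures agree.

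Keeping the untruncated planned dose over 4 weeks would also give 100% on QW and Q2W, but not in Cycle 1: a compliant participant ending at C1D4 would show 44/68 = 65%.

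The cost is two short wording edits and the matching programming; no new data are needed.
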